## **C6.0** Blood specimen collection (optional)

Blood samples will be collected on the day of registration after signing informed consent to collect blood annually for up to five years. For subjects found to have lung cancer, a blood specimen will be obtained prior to treatment and 3 to 6 months post treatment (for those who will be given treatment

with curative intent) to determine whether the biomarkers decrease after treatment with curative intent. Blood samples will be drawn without regard to fasting status or time of day, although the time of day and approximate time of last meal will be recorded on the sample collection form.

The first one mL blood contain contaminating substances from epithelial cells will be discarded. One 9 mL blood sample (obtained from a 10 cc Red uncoated blood tube) will be drawn and processed into serum and clot. One 9 ml blood sample obtained from a 10 cc yellow-top ACD tube and one 9 ml blood sample obtained from a lavender-top 10 mL potassium EDTA tube will be drawn and processed into plasma for the biomarkers measurements. Part of the buffy coat will be used for cell sorting to study the composition of the immune cells with the remaining stored for DNA-based biomarker assessments. The time between blood collection and storage will be recorded.

Samples that are more than 2 hours between collections, processing and storage will be repeated. A unique identifier will be associated with each specimen and linked to the patient data in the CC database management office. The samples will be stored at -80°C.

# C7. Thoracic Low-dose Computed Tomography (LDCT)

A multi-detector row CT scanner with minimum section collimation of ≤1 mm and minimum number of data acquisition channels ≥ 16 will be employed. The CT scans will be performed at 120 kV, 40-50 mA (automatic modulation based on patient size), pitch 1:0, gantry rotation time ≤0.5 seconds (total scan times <15 seconds). The scan length will be from the lung apices to the adrenals. Low radiation dose acquisitions using less than ≤1.5 mSv effective dose will be obtained using reduced mA and a minimum gantry rotation time. The CT dose index volume (CTDIvol) will be ≤3.0 mGy (32cm) for a standard sized patient (170 cm, 70 Kg, BMI = 24). Images will be acquired in a single inspiratory breath hold with the subject in the supine position with arms overhead. No intravenous or oral contrast will be used. Images will be reconstructed using 1 mm or less section thickness and ≤1 mm spacing. Two image reconstruction algorithms will be employed, a high spatial frequency algorithm for lung parenchyma (e.g. bone (GE) or B60 (Siemens)) and an intermediate spatial frequency algorithm for mediastinal structures (e.g. standard (GE) or B35 (Siemens)). The mediastinal reconstruction algorithm will be useful to provide lower noise images on these reduced dose images. Images will be archived to the hospital/screening center based PACS server with full annotation and stored in local site for clinical use if needed. A second image file will be saved with an anonymized study number. The file with the anonymized study number will be sent to the central study data server.

Calibration scans will be performed at all participating sites using the body calibration phantoms and spatial resolution supplied with the CT scanners at each site. These calibration scans will be performed using the same technical parameters as proposed in the low dose CT protocol (kVp 120, 40 mAs, rotation time 1 second or less, 32 cm field of view reconstruction, intermediate and high spatial frequency reconstruction algorithm). Spatial resolution and image noise will be measured on the submitted images and used for standardization of each site. Reference scans will be repeated on a yearly basis. [name] and [name], the VGH Radiation Protection Officer and Medical Physicist will review the data to ensure adequate scanner performance at each of the sites.

#### **C8. LDCT Reading and Reporting**

The LDCTs will be processed by computer assisted detection (CAD) software (Philips or the Mevis Veolity system). The software will automatically identify lung nodules ≥3 mm in diameter, determine the location, define the nodule type (solid, semisolid, non-solid, perifissural), measure the short and long axis, volume and calculate the nodule malignancy risk score according to the PanCan calculator.8 A trained radiology technician will review the CAD marks. The technician reviewed the processed cases and the annotated markings of abnormalities by the CV software. CAD marks on true nodules will be accepted and false positives CADS marks deleted. The technician then reviews the scans and manually marked any additional nodules and other abnormalities that are not identified by the CAD software. The LDCT scans will be read by a chest radiologist who has read at least 300 chest CTs in the last 3 years. On alternate days, the radiologist will either report the scans with the CAD marks displayed or first report the findings without the CAD marks displayed and then with the CAD marks displayed. The time taken to generate a report with the CAD marks displayed, without the CAD marks will be automatically tracked by the computer. Changes in the report for scans that are read without the CAD marks displayed first will be recorded. A standardized report will be made similar to that in Figure 8. The report will be sent to the Screening Center Physician and the participants' primary care physicians. The report will contain a recommendation for follow-up or referral to a respirologist/thoracic surgeon in the screening program for further investigation.

## **C9.** Management of Abnormal Scans

CT scan follow up protocol will be determined by the schema in Section C1 (Figure 7). Participants with no abnormality on the baseline exam or lung nodule with a maximum malignancy risk

score <1.5% will have a repeat scan in 24 months. For participants with a maximum nodule malignancy risk score of 1.5% to <6% will have a repeat LDCT annually for 2 years (for solid nodules) and up to 5 years (for sub-solid nodules). Those with malignancy score 6% to 10% will have a repeat LDCT in 3 months organized by the study navigator. Participants with a nodule malignancy risk score ≥10% will be considered suspicious for lung cancer. A nodule that grows on two consecutive scans (>1.5 mm in mean diameter, volume change (≥100% for nodules <5 mm; ≥30% >5 mm but ≤10mm and ≥20% for nodules ≥10 mm), volume doubling time between 30 to 400 days or development of a solid core ≥5 mm in a sub-solid nodule) will also be considered to be suspicious for lung cancer. They will be seen by the study physician/surgeon. A shared decision will be made regarding additional imaging studies (repeat LDCT or PET/CT) or a biopsy (bronchoscopic transbronchial biopsy or CT guided transthoracic needle/core biopsy). Further diagnostic procedure may include serology for cryptococosis and histoplasmosis or wedge resection. The overall aim will be to establish a pathologic or cytologic diagnosis and perform definitive treatment. Any confirmed diagnosis of lung cancer and other abnormality on the CT in the surrounding soft tissue of the chest and abdomen will be treated or followed up according to standard of care in the institution as directed by the medical team and the local study radiologist.

# C10. Smoking Cessation

Smoking cessation will be offered to all current smokers whether they are eligible or not eligible for the study. Although randomized controlled trials did not find a statistically significant difference between individuals who were screened with CT and individuals who were not screened, 62-,64 a three to five times higher smoking cessation rate was observed compared with spontaneous quit rate in the general population which is generally between 2% to 3%. 64,65 In the multi-center PanCan study of 2,537 participants, the smoking cessation rate (confirmed by urine cotinine) was 21% at the end of 12 months and 25% at the end of 24 months. Only 5% of the former smokers re-started smoking. The higher smoking cessation rates in a CT screening program were often attributed to a "teachable moment". It was found that participants who were presented with abnormal CT results had a higher smoking cessation rate than those with normal scan. 62,66,67 The differences in smoking prevalence between those with abnormal screen versus normal screen were present up to 5 years after the last screen. 67 Personal perception of increased health risk from visualization of abnormalities on a CT scan may improve smoking cessation rate compares to conventional approach using counseling with and without pharmacotherapy. Since the information from a screening CT can be readily extracted, we will use a

combination of counseling (Canadian Quit Now Smoking Cessation Program or Quitline in Australia) with nicotine replacement and other smoking cessation drug such as buproprion or varenicline as needed; plus use of personalized CT images of lung nodules, emphysema and or coronary artery calcification. The CT scans will be analyzed by the VIDA Diagnostic software to generate a 3D image display of the severity of their emphysema (Figure 9). Pulmonary nodules and coronary artery calcification will be extracted from their CT scans (Figures 10 and 11). The abnormal findings will be explained to the smokers. They will receive a hard copy of the relevant images. The participants will be followed up in person 3, 6 and 12 months after intervention to assess their smoking status. Smoking cessation will be confirmed by urinary cotinine measurement or exhaled carbon monoxide. Resumption of smoking among former smokers will be monitored using urine cotinine monitoring at baseline and the annual visits.

#### C11. Outcome Evaluation

The outcomes of interest in this study are:

- the number needs to be screened to detect one cancer with the PLCOm2012 versus the USPSTF selection criteria
- proportion of participants who do not meet either the PLCOm2012 or USPSTF screening selection criteria but develop lung cancer
- cancer detection rate
- the number of interval lung cancer cases
- recall rate
- Invasive procedure rate
- Non-malignant biopsy/surgery rate
- adverse events (morbidity related to bronchoscopy, biopsies, surgery or other treatments)
- resection rate
- stage distribution of the lung cancers
- Mortality (lung cancer, all causes)
- smoking cessation rate (for current smokers)
- rate of detection of other incidental significant treatable diseases
- type and costs of downstream investigation and treatment related to abnormalities found by the screening procedures whether the final diagnosis is lung cancer or not

identify logistics/barriers for an early detection program

The participants will be followed regularly at annual intervals for four years either by telephone or personal visits, and details of all outpatient visits and use of allied health services related to lung cancer diagnosis or treatment will be obtained. Additional information regarding development of lung cancer or death from lung cancer beyond 4 years will be obtained from Cancer Registries and Death Registries. Change in smoking status will be monitored annually using urinary cotinine/exhaled carbon monoxide.

Diagnostic procedures related to the early detection procedures will be tracked by the site study coordinator. The lung cancer cases will be evaluated by the Steering Committee. The histology cell type, TNM stage, treatment procedures, length of hospital stay, type of hospital ward (Intensive Care, stepdown unit, general ward), physician visits etc. will be tracked by the site study coordinator and submitted to the CC database. For lung cancer cases (both prevalent and interval) that are not managed by the site investigators, the site coordinator will obtain the procedure and pathology reports as well as the tissue blocks from the outside facility for review.

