# A6. Frequency and Duration of LDCT Screening

The optimal frequency and duration of LDCT screening has not been defined. NLST has 3 rounds of screening one year apart. The current USPSTF recommendation is annual LDCT screening until the age of 80 if the person is healthy and fit for surgery if early lung cancer is found. Screening will be discontinued after 15 years of smoking abstinence. The UK Lung Cancer Screening Trial has a single round of CT screening. Data from the PanCan study suggests that screenees with no lung nodules greater than 1 mm or a lung nodule malignancy risk <1.5% in the largest nodule (if more than one lung nodule) has very low risk for lung cancer within 2 years (Figure 5). We will offer a second round of LDCT screening in 24 months to those without lung nodule or the lung nodule malignancy score is <1.5%.

Those with lung nodules with a risk score ≥1.5% will be followed for 2 years (solid nodules) and up to 5 years (sub-solid nodules) according to current clinical practice. All participants will be prospectively followed by phone, letter or personal interview for a minimum of 6 years to determine occurrence of incident lung cancer. If evidence warrants, the follow-up protocol will be amended.

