# C13. Statistical Considerations

C13.1 In the PLCO intervention arm smokers, the mean PLCOm2012 estimated 6-year lung cancer risk was 3.9%. This suggests that in a similar sample of 4000 smokers screened and followed for six years, 155 lung cancers would be detected. Assuming that 85.3% and 77.8% of the samples will be positive by the USPSTF criteria and PLCOm2012 risk>1.51% criteria, respectively, and that the sensitivity to detect

lung cancer are 83.8% and 94.3%, respectively, our sample size of 4000 will have greater than 90% power to demonstrate that compared to the USPSTF criteria, the PLCOm2012 criteria selects a significantly smaller proportion of individuals and detects a significantly higher proportion of lung cancers. Our study will have a 39% power to demonstrate that the positive predictive power for PLCOm2012 (4.2%) is significantly greater than observed for the USPSTF (3.4%). The numbers used in these calculations come directly from PLCO data. A two-sided alpha error of 0.05 was applied. The correlation between the two criteria was -.222. Power calculations were performed using STATA MP 14.1 software (College Station, Texas) using bootstrap resampling methods and the *power pairedproportions* program based on McNemar's test.

C13.2 For screening CT detected lung nodules, the retrospective analysis by van Riel et al suggest the PanCan nodule management protocol may have better sensitivity and specificity than Lung-RADS . (Figure 3, 4). Each management schema has unique harms and benefits with possible costs differences so we will undertake a prospective comparison of the PanCan probabilistic strategy and the LungRADS nodule classification. Since the Lung-RADS also recommend using the PanCan nodule protocol for class 4 findings, a randomized trial comparing the two would not be meaningful. We will determine their effect on the frequency of additional imaging, biopsies, surgical resection, and outcomes of these procedures (diagnosis, False positives, False negatives). Through an iterative process, the management protocols will be evaluated every six months to determine if revision is warranted).

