# D. TIME LINE By Year

- Ethics, DSM appointment, site coordination /activation at all sites, commence recruitment and LDCT screening for all cohorts, begin collation of data at all sites.
- 2 Continue recruitment and screening at all sites. Complete screening by mid-year. Follow-up of cohort and outcomes of screening throughout year, begin collation of data at all sites.
- Follow-up of cohort and outcomes throughout year; continue collation of data at all sites and collation of findings across cohorts, begin economic evaluation. CAD substudy evaluation.
- 4 Follow-up, interim reports; continue economic evaluation.
- 5 Completion of follow-up, finalise collation of data across all sites, finalise economic evaluation, presentation and publication of reports

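### The sensitivity and PPV power rests on six years of follow-up per participant, but the timeline closes follow-up in Year 5, when participants have only about 3 to 5 years

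*Protocol*

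**What the plan says.** - **C13.1 (Statistical Considerations)** sets the event count: "in a similar sample of 4000 smokers screened and followed for six years, 155 lung cancers would be detected". The claim of more than 90% power covers the proportion selected and the sensitivity; power for PPV is given as 39%.
- **A6, Frequency and Duration of LDCT Screening** (the second section numbered A6) has all participants followed by phone, letter or interview "for a minimum of 6 years to determine occurrence of incident lung cancer".
- **C11 (Outcome Evaluation)** states: "The participants will be followed regularly at annual intervals for four years either by telephone or personal visits". Its next sentence moves ascertainment of lung cancer and lung cancer death after four years to cancer and death registries, with no closing date.
- **D (Time Line)** gives Year 5 as "Completion of follow-up, finalise collation of data across all sites", together with publication. Its entry for Year 2 includes "Complete screening by mid-year".
- **C3 and E3** set accrual of 4,000 participants over 24 months.
- **C9**, like the Frequency and Duration section, schedules a repeat scan at 24 months for participants without nodules or with a low nodule risk score.

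**The concern.** Aim 1 tests a selection rule defined by a six-year risk. Its power statement counts cancers over six years, yet the only dated end of follow-up comes before any participant can have six years. If the final analysis is run as section D schedules it, three things follow:

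- Sensitivity and PPV would be estimated over a window that differs between participants and is shorter than the one that defines the rule.
- The expected number of cancers, which is the effective sample size for the sensitivity comparison, could fall short of the 155 assumed.
- The definitive Aim 1 analysis would have no agreed date.

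Two further mismatches sit beside this one. The Frequency and Duration section and C11 differ on how long participants are contacted directly (six years against four). Completing screening by the middle of Year 2 fits neither 24 months of accrual nor a repeat scan at 24 months.

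**Working it through.** **1. The protocol's own figures.** C13.1 states that "the mean PLCOm2012 estimated 6-year lung cancer risk was 3.9" per cent. Then 4,000 × 0.039 = 156, against 155 stated, so the count reproduces and is a six-year count. Treating the two selected groups as unpaired, with 0.853 × 4,000 = 3,412 and 0.778 × 4,000 = 3,112 people, PPVs of 3.4% and 4.2% give 39.5% power, against 39% stated.

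**2. Follow-up at the end of Year 5.** Assume uniform entry from the start of Year 1.

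- Entry over months 0 to 24, closing at month 60: 36 to 60 months, mean 48 (4.0 years).
- Entry over months 0 to 18 (if entry ended mid-Year 2): 42 to 60 months, mean 51 (4.25 years).

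Nobody reaches 72 months. Year 1 also contains ethics approval and site activation, so a later start would shorten these figures.

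**3. Cancers, pro-rated under a constant hazard (assumption).**

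- 4.0 years: 4,000 × 0.039 × 4/6 = 104.
- 4.25 years: 4,000 × 0.039 × 4.25/6 = 110.5, about 111.

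Against 155, this is a fall of about 29% to 33%.

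**4. Power for sensitivity.** C13.1 assumes that the sensitivities to detect "lung cancer are 83.8% and 94.3%, respectively", for USPSTF and PLCOm2012. With n cancers, d = 0.943 − 0.838 = 0.105 and t the discordant proportion among cases, large-sample McNemar power is

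Φ[(d√n − 1.96√t) / √(t − d²)], where t = p1 + p2 − 2·p11 and p11 = p1·p2 + ρ·√(p1(1−p1)·p2(1−p2)).

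The stated correlation of −0.222 cannot be used here. The smallest joint probability is 0.838 + 0.943 − 1 = 0.781, which gives a minimum correlation of (0.781 − 0.7902)/0.0854 = −0.108. The value −0.222 is instead the minimum for the selection proportions of 85.3% and 77.8%. The within-case correlation is therefore unknown and a range is needed.

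| Within-case correlation | t | 155 cancers | 104 cancers |
|---|---|---|---|
| −0.108 (lowest feasible) | 0.219 | 80% | 63% |
| 0 | 0.201 | 84% | 67% |
| 0.196 (set so that 155 gives 90%) | 0.167 | 90% | 75% |
| 0.559 (highest feasible) | 0.105 | 99% | 92% |

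As an example, the first row at 104 cancers is (0.105 × 10.198 − 1.96 × 0.468)/√(0.219 − 0.011) = 0.337, and Φ(0.337) = 0.63. At 111 cancers the third row gives 78%. Simulating the uncorrected McNemar test gives values 2 to 4 points higher across the correlations tried (−0.108, 0 and 0.2) and the same pattern.

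**5. Power for PPV.** Scaling 3.4% and 4.2% by 4/6 or 4.25/6 takes power from 39% to 28% or 29%.

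**6. Power for the proportion selected.** C13.1 writes: "Assuming that 85.3% and 77.8% of the samples will be positive by the USPSTF criteria and PLCOm2012 risk>1.51% criteria". This is a comparison at baseline on 4,000 people. With t = 0.853 + 0.778 − 2 × 0.631 = 0.369 and d = 0.075, power exceeds 99% whatever the follow-up.

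**The case against.** The strongest objection concerns the event count. Screening brings diagnoses forward, so pro-rating a six-year risk may understate early cancers. Section A1 reports that the earlier Canadian screened cohort had 6.5% confirmed cancers at a median of 3.8 years, against a predicted six-year risk of 4.5%. Applied here, that is 0.065 × 4,000 = 260 cancers, or about 225 after scaling by 3.9/4.5. Both exceed 155. This stands: a loss of events at Year 5 is possible but not established. It does not cure the mismatch between the analysis window and the six-year risk.

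A reader might infer that C11 stops cancer ascertainment at four years. It does not. Four years is the direct-contact phase, and registries continue with no stated end, which is compatible with six years. What remains is the disagreement with the Frequency and Duration section on direct contact.

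A reader might also set 63% against the claimed power of more than 90% and blame follow-up for the whole gap. That mixes two effects. At the correlation that yields 63%, the protocol's own 155 cancers already give only 80%.

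Nor does the mid-Year-2 line show that accrual would stop at about 3,000 people. C3 and E3 both fix 4,000 over 24 months, and the timeline states no cut in recruitment.

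The second phase could be said to restore the events: 8,000 people at four years would give about 208 cancers. But it awaits institutional approval, and the power statement is written for 4,000.

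Finally, Year 5 might be only a funding milestone. However, section D places interim reports in Year 4 and completion in Year 5, and schedules nothing later.

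**Conclusion.** The contradiction holds and needs correcting. C13.1 and the Frequency and Duration section rest on six years; section D ends follow-up and publishes when participants have 3 to 5 years. The sections also disagree on direct contact, and the mid-Year-2 end of screening disagrees with accrual and with the 24-month scan.

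The firm consequence is the window: at Year 5, sensitivity and PPV would not refer to the six-year risk that defines the rule. The effect on power is conditional. Given uniform entry from the start of Year 1 and a constant hazard, about 104 to 111 cancers replace 155. Like for like at 104 cancers, sensitivity power drops by about 15 to 17 points for correlations from −0.108 to 0.196, and by less at the highest feasible correlation, where it stays at about 92%. PPV power, already low, falls to about 28% to 29%. The part of the power claim that concerns the proportion selected is untouched. The documents do not support a statement that the study will certainly have fewer cancers than planned.

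**What to change.** 1. Define the Aim 1 outcome as lung cancer within six years of each participant's baseline, with years 5 and 6 taken from the cancer and death registries that C11 already names, and give the registry ascertainment a closing date.
2. Align the Frequency and Duration section, C11, C13.1 and section D with that window, and state one length and method of direct contact.
3. Label the Year-5 report as interim. Give its own expected cancers (about 104 to 111 under a constant hazard, with the earlier cohort's experience as an upper scenario) and a power range over feasible within-case correlations.
4. Reconcile the mid-Year-2 screening line with 24-month accrual and the second-round scan.

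The cost is revised wording and a later registry extract. The drawback is time: the last participant enters at month 24 and reaches six years at month 24 + 72 = 96, the end of Year 8, so the definitive Aim 1 result comes about three years after the Year-5 report.

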- C4.2.2.2 Non eligible people who expressed an interest to be screened but do not meet either screening inclusion criteria or are excluded for other reasons will be asked to take part in long term follow up.
- C4.2.2.3 In addition, those who are eligible for screening but decline to take part after a discussion about the risks and benefits will be offered participation in long term follow up.

We will seek consent for long term linkages studies on these groups (C4.2.2.2 and C4.2.2.3) of participants using an opt-out process.

In Australia, consent will be sought to link participant data with state-based cancer registries and the National Death Index and MBS records in order to determine the incidence of lung cancer in those who do not fulfill the screening inclusion criteria and also to assess whether those who are not eligible subsequently undergo CT scanning outside of the study.

In Canada, consent will be sought to link participant data with the Cancer Registry.

Participants will be offered the opportunity to opt out at any time including at the time of the telephone interview, those who do not opt out at this point will be sent a participant information sheet and opt out form and asked to return to the study centre by pre-paid envelopes if **they do not** wish to take part in the linkages study. They will be asked to return the form within 3 weeks and if a form has not been received within that time frame it will be assumed that they do not object to participation in the linkages study.

Consent may also be sought for participation in Optional Sub-studies such as air pollution surveys, biomarkers and quality of life.

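### C11 names registries only for events beyond year 4, so in screened participants cancers diagnosed elsewhere and deaths before then rest on annual contact

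*Protocol*

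**What the plan says.** C11 sets the active follow-up: "The participants will be followed regularly at annual intervals for four years either by telephone or personal visits". The next step is registry based and tied to a later period: "Additional information regarding development of lung cancer or death from lung cancer beyond 4 years will be obtained from Cancer Registries and Death Registries". The deaths named there are lung cancer deaths, although the outcome list in the same section includes mortality from all causes as well as the number of interval lung cancers.

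The second section numbered A6 (Frequency and Duration of LDCT Screening) gives another length and names no registry: "All participants will be prospectively followed by phone, letter or personal interview for a minimum of 6 years". The time line in section D completes follow-up in year 5.

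C4.2 describes linkage for people who are not screened, namely those who are ineligible and those who are eligible but decline: "We will seek consent for long term linkages studies on these groups (C4.2.2.2 and C4.2.2.3) of participants using an opt-out process". No time limit is attached. In Australia it covers state cancer registries, the National Death Index and MBS records, and one stated aim is "in order to determine the incidence of lung cancer in those who do not fulfill the screening inclusion criteria". For Canada the text reads: "In Canada, consent will be sought to link participant data with the Cancer Registry". No Canadian death registry is named there.

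Contact is not the only source in years 0 to 4. C9 schedules repeat scans, and C11 adds: "Diagnostic procedures related to the early detection procedures will be tracked by the site study coordinator". C11 also has the coordinator collect procedure and pathology reports for cancers managed elsewhere, but does not say how such a case comes to notice.

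**The concern.** Followed as written, the protocol uses different sources over the same years according to whether a person was screened. Unscreened people can be found in a registry from the start. A screened person whose cancer is diagnosed at an outside hospital between scans, or who dies, is found in years 0 to 4 only if the annual contact reaches the participant or someone who can report the event. People who are very ill or have died are plausibly the hardest to reach.

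Two kinds of result are exposed. The first is the count of interval cancers and deaths. C9 gives participants with no abnormality, or a maximum nodule score below 1.5%, their next scan at 24 months, and C13.2 reviews the management protocols every six months. An undercount of interval cancers would make the current scheme look safer at those reviews than it is. The second is any quantity that puts screened and unscreened cases in one denominator: absolute sensitivity, and the C11 outcome on people who meet neither criterion but develop lung cancer.

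**Working it through.** **1. The protocol's own case count.** C13.1 gives a mean six-year risk of 3.9% and 4,000 smokers: 4,000 × 0.039 = 156, against 155 stated. It reproduces.

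**2. Cases in years 0 to 4.** Spread evenly over six years: 155 × 4/6 = 103.3, about 103. The even spread is an assumption. LDCT may bring diagnoses forward, but the cancers it brings forward are those that the study finds itself.

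**3. Cases exposed to the gap.** Only cancers arising outside the screening pathway depend on contact. The protocol gives neither their share nor a contact failure rate, so both are assumed: share f from 20% to 50%, and missed fraction m from 5% to 30%.

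- Exposed cases = 103 × f: 103 × 0.20 = 21 to 103 × 0.50 = 52.
- Lost cases = 103 × f × m: 103 × 0.20 × 0.05 = 1.0 to 103 × 0.50 × 0.30 = 15.5, so about 1 to 15.
- As a fraction of the cancers outside the pathway, the loss is m itself: 5% to 30%.

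**4. Absolute sensitivity and the neither-criterion share.** Let q be the true share of all cancers in people meeting neither criterion, with those cases fully linked, and let u be the fraction missed among criterion-positive cases. The observed neither share is q / [(1 − q)(1 − u) + q]. Each sensitivity is multiplied by k = (1 − u) / [(1 − q)(1 − u) + q]. At the top of step 3, u = 15/155, about 0.10. The protocol does not give q for the pool approached, so 2% and 10% are assumed.

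- q = 2%: the denominator is 0.98 × 0.90 + 0.02 = 0.902. The neither share reads 0.02/0.902 = 2.2%, and k = 0.90/0.902 = 0.998.
- q = 10%: the denominator is 0.90 × 0.90 + 0.10 = 0.91. The neither share reads 0.10/0.91 = 11.0%, and k = 0.90/0.91 = 0.989.

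If missing does not depend on which criterion was met, both sensitivities carry the same k and their ratio is unchanged.

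**5. The paired comparison.** McNemar's test uses only cases positive on exactly one criterion. Neither-criterion cases do not enter it, and cases on both sides of the comparison come mainly from the same screened cohort. What remains is a smaller number of cases. With the C13.1 sensitivities of 83.8% and 94.3%, and the correlation set to 0 for illustration, the discordant proportions are 0.0478 and 0.1528, their difference d = 0.105 and their sum D = 0.2006. Power = Φ[(d√n − 1.96√D) / √(D − d²)].

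- n = 155: (1.307 − 0.878)/0.435 = 0.99, power about 84%.
- n = 140 (15 lost): (1.242 − 0.878)/0.435 = 0.84, power about 80%.

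This measures the change from losing cases. It does not re-run the protocol's power calculation, which also used bootstrap resampling and another correlation.

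**The case against.** The strongest reply is that the study sees most of what matters without a telephone call. Repeat scans are scheduled, suspicious findings go to the study physician or surgeon, and coordinators track procedures, stage and treatment. In Australia, C14.2 also draws Medicare and public hospital use for costing. A reader might infer that every early cancer is known only through contact. The documents do not support that, and applying a contact failure rate to all 103 cancers would wrongly include those found by screening. A missed call can also be made good a year later.

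It can also be said that C11 does not forbid earlier registry records, and that an extract taken after year 4 could return earlier diagnosis dates. That is true, but the text does not say so, and it would come too late for the six-monthly reviews.

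A reader might infer from C4.2 that screened participants give no consent to linkage. This cannot be concluded: the consent forms are not available here, and C11 already presupposes registry use for people under follow-up. The contrast between screened and unscreened people also comes from reading C11 and C4.2 together. C11 speaks of participants in general, and the Canadian sentence does not restate which group it covers.

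Finally, the head-to-head comparison of the two criteria is largely insulated. That stands. What also stands is that, for screened participants in years 0 to 4, no systematic source other than contact is stated for cancers diagnosed elsewhere and for deaths.

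**Conclusion.** The point holds in limited form. It concerns data collection, and an analysis plan cannot recover events that were never gathered. On assumed rates, about 1 to 15 of roughly 103 cancers in years 0 to 4 would be missed. That is small for the total but amounts to 5% to 30% of the cancers arising outside the pathway, which include the interval cancers. Deaths are exposed in the same way, and all-cause death is not among the items to be taken from registries even after year 4. Absolute sensitivity shifts by about 1% or less in relative terms under the values tried, and the neither-criterion share by up to one percentage point. The documents do not support the stronger reading that the PLCOm2012 versus USPSTF result would be biased. The follow-up lengths in C11, A6 and section D also disagree, while the count of 155 rests on six years.

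**What to change.** State in C11 that every consenting participant, screened or not, is linked to the cancer and death registries from the date of enrolment, for all-cause as well as lung cancer death. Take the case date as the earliest of contact report, site record or registry record, and keep the annual contact as a supplement. Name the death source for Canada in C4.2. Reconcile the four years in C11, the minimum of six years in A6 and completion in year 5 in section D.

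The cost is mainly a wider date range in linkages already planned across several jurisdictions. If the consent forms do not already cover it, wording must be added, and new wording would not by itself cover people already enrolled.
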